6.4.1.2 Detailed Study Procedures

Study Day 0 (Day of Inoculation with Test Article)

1. Verify that Informed Consent was obtained and that the consent form was signed by both the subject and by the study staff.
2. Verify that all applicable eligibility criteria have been met.
3. Collect 3.5mL to perform serum β -HCG testing (females only). Ensure the test is negative before proceeding; a positive test will exclude the subject from the study as per protocol, Section 4.2.
4. Obtain a nasopharyngeal (NP) or mid-turbinate swab to test for SARS-CoV 2 – the virus that causes COVID-19 – from all volunteers regardless of vaccination status based on guidance from federal, state, local, and/or institutional health officials* or at the discretion of the clinician (may be collected up to 72 hours in advance of stated collection time).

*This guidance may be informed by the local COVID infection rate, severity of infections, vaccination rates, and other factors as the COVID-19 pandemic continues to evolve and change.

5. Perform interim history, including sexual history, and focused physical exam, concentrating on any acute complaints. Physical exam may extend beyond focused if indicated by complaint or physical finding.
6. Admit the volunteer to the inpatient unit.
7. Record vital signs (blood pressure, temperature, heart rate, and respiratory rate) twice a day.
8. Review and document concomitant medications.
9. Obtain approximately 57 mL of blood for CBC with differential, virus isolation and culture from serum and whole blood (PCR/culture), and immunology (serum, plasma, peripheral blood mononuclear cells [PBMCs]), and PAXGene. These laboratory studies are drawn as baseline values and will not determine eligibility.
10. Obtain 5 mL of clean-catch urine for virus isolation & culture.

11. Obtain cervico-vaginal secretion or semen sample for virus isolation & culture.
12. Obtain saliva sample for virus isolation and culture.
13. Review pregnancy prevention with the subject.
14. Obtain oral fluid for serology (CIR site only).
15. Administer the test article.
16. Observe for at least 30 minutes after inoculation and evaluate for immediate hypersensitivity.
17. Provide education by study staff describing the signs and symptoms of potential AEs, and how and when to contact study staff.

Study Day 1

1. Perform interim history and focused physical exam, concentrating on any acute complaints.
2. Record vital signs twice a day.
3. Obtain approximately 15 mL of blood for virus isolation from serum and whole blood (PCR and culture) and PAXGene.

Study Day 2

1. Perform interim history and focused physical exam, concentrating on any acute complaints.
2. Record vital signs twice a day.
3. Obtain approximately 15 mL of blood for virus isolation from serum and whole blood (PCR and culture).
4. Obtain clean-catch urine for virus isolation (PCR/culture).
5. Obtain saliva sample for virus isolation (PCR/culture).
6. Obtain 2 mL of blood for PAXGene.

Study Day 3

1. Perform interim history and focused physical exam, concentrating on any acute complaints.
2. Record vital signs twice a day.
3. Obtain approximately 15 mL of blood for virus isolation from serum and whole blood (PCR and culture) and PAXGene.

Study Day 4

1. Perform interim history and focused physical exam, concentrating on any acute complaints.
2. Record vital signs twice a day.

3. Obtain approximately 47 mL of blood for CBC with differential, virus isolation from serum and whole blood (PCR/culture), immunology (serum, plasma, PBMCs), and PAXGene.
4. Obtain clean-catch urine for virus isolation (PCR/culture).
5. Obtain cervico-vaginal secretion or semen sample for virus isolation (PCR/culture).
6. Obtain saliva sample for virus isolation (culture/PCR).
7. Obtain oral fluid for serology (CIR site only).

Study Day 5

1. Perform interim history and focused physical exam, concentrating on any acute complaints.
2. Record vital signs twice a day.
3. Obtain 13 mL of blood for virus isolation from serum and whole blood (PCR/culture).
4. Cohorts 3 and 4: Perform mosquito feeding on subset of volunteers.

Study Day 6

1. Perform interim history and focused physical exam, concentrating on any acute complaints.
2. Record vital signs twice a day.
3. Obtain approximately 15 mL of blood for virus isolation from serum and whole blood (culture/PCR) and PAXGene.
4. Obtain clean-catch urine for virus isolation (PCR/culture).
5. Obtain saliva sample for virus isolation (PCR/culture).
6. Obtain oral fluid for serology (CIR site only).
7. Cohorts 3 and 4: Perform mosquito feeding on subset of volunteers.

Study Day 7

1. Perform interim history and focused physical exam, concentrating on any acute complaints.
2. Record vital signs twice a day.
3. Obtain 13 mL of blood for virus isolation from serum and whole blood (PCR/culture).
4. Cohorts 3 and 4: Perform mosquito feeding on subset of volunteers.

Study Day 8

1. Perform interim history and focused physical exam, concentrating on any acute complaints.
2. Record vital signs twice a day.
3. Obtain approximately 52 mL of blood for CBC with differential, AST, ALT, serum creatinine, virus isolation from serum and whole blood (culture/PCR), immunology (serum, plasma, PBMCs), and PAXGene.
4. Perform serum β-HCG testing (females only).

5. Obtain clean-catch urine for virus isolation (PCR/culture).
6. Obtain cervico-vaginal secretion or semen sample for virus isolation (PCR/culture).
7. Obtain saliva sample for virus isolation (PCR/culture).
8. Obtain oral fluid for serology (CIR site only).

Study Day 9

1. Perform interim history and focused physical exam, concentrating on any acute complaints.
2. Record vital signs.
3. Obtain 13 mL of blood for virus isolation from serum and whole blood (PCR/culture).
4. Review pregnancy prevention and continued use of barrier contraceptives.
5. Provide volunteer with diary card to record temperature twice a day.
6. Provide education by study staff describing proper use of thermometer and memory card.
7. Provide education by study staff describing the signs and symptoms of potential AEs, and how and when to contact study staff.
8. Provide subjects with insect repellent and education on how to prevent mosquito bites (May – October).
9. **May discharge from inpatient unit if subject meets discharge criteria (Section 6.4.2).**

Study Day 10 (+ 1 day from 10 days following test article administration)

1. Perform interim history, including sexual history, and focused physical exam, concentrating on any acute complaints.
2. Record vital signs from subject diary card and perform vital signs.
3. Obtain approximately 15 mL of blood for PAXGene and virus isolation from serum and whole blood (PCR/culture).
4. Obtain clean-catch urine for virus isolation (PCR/culture).
5. Obtain cervico-vaginal secretion sample for virus isolation (PCR/culture).
6. Obtain saliva sample for virus isolation (PCR/culture).
7. Obtain oral fluid for serology (CIR site only).
8. Perform serum β -HCG testing (females only).
9. Review pregnancy prevention and continued use of barrier contraceptives.

Study Day 12 (\pm 1 day from 12 days following test article administration)

1. Perform interim history, including sexual history, and focused physical exam, concentrating on any acute complaints.
2. Record vital signs from subject diary card and perform vital signs.
3. Obtain approximately 22 mL of blood for CBC with differential, AST, ALT, serum creatinine, virus isolation from serum and whole blood (PCR/culture), and PAXGene.

4. Obtain clean-catch urine for virus isolation (PCR/culture).
5. Obtain cervico-vaginal secretion or semen sample for virus isolation (PCR/culture).
6. Obtain saliva sample for virus isolation (PCR/culture).
7. Obtain oral fluid for serology (CIR site only).
8. Perform serum β -HCG testing (females only).
9. Review pregnancy prevention and continued use of barrier contraceptives.

Study Day 14 (\pm 1 day from 14 days following test article administration)

1. Perform interim history, including sexual history, and focused physical exam, concentrating on any acute complaints.
2. Record vital signs from subject diary card and perform vital signs.
3. Obtain approximately 45 mL of blood for immunology (serum, plasma, PBMCs), PAXGene, and virus isolation from serum and whole blood (PCR/culture).
4. Obtain clean-catch urine for virus isolation (PCR/culture).
5. Obtain cervico-vaginal secretion sample for virus isolation (PCR/culture).
6. Obtain saliva sample for virus isolation (PCR/culture).
7. Obtain oral fluid for serology (CIR site only).
8. Perform serum β -HCG testing (females only).
9. Review pregnancy prevention and continued use of barrier contraceptives.

Study Day 16 (\pm 1 day from 16 days following test article administration)

1. Perform interim history, including sexual history, and focused physical exam, concentrating on any acute complaints.
2. Record vital signs from subject diary card and perform vital signs.
3. Obtain approximately 22 mL of blood for CBC with differential, AST, ALT, serum creatinine, virus isolation from serum and whole blood (PCR/culture), and PAXGene.
4. Perform serum β -HCG testing (females only).
5. Obtain clean-catch urine for virus isolation (PCR/culture).
6. Obtain cervico-vaginal secretion or semen sample for virus isolation (PCR/culture). (Cervico-vaginal cup may be inserted at home by the volunteer prior to presentation to the clinic).
7. Obtain saliva sample for virus isolation (PCR/culture).
8. Obtain oral fluid for serology (CIR site only).
9. Review pregnancy prevention and continued use of barrier contraceptives.

Study Day 21 (\pm 1 day from 21 days following test article administration)

1. Perform interim history, including sexual history, and focused physical exam, concentrating on any acute complaints.

2. Record vital signs.
3. Perform serum β -HCG testing (females only).
4. Review pregnancy prevention and continued use of barrier contraceptives with all subjects.
5. Obtain approximately 40 mL of blood for immunology (serum, plasma, PBMCs), PAXGene and virology* from serum and whole blood (PCR/culture). CBC will be done if prior white blood cell count (WBC), ANC, platelet count, or hemoglobin results are a Grade I or above and unresolved, as defined by protocol, on Study Day 16.
6. Obtain clean-catch urine for virus isolation (PCR/culture).
7. Obtain cervico-vaginal secretion or semen sample for virus isolation (PCR/culture). (Cervico-vaginal cup may be inserted at home by the volunteer prior to presentation to the clinic).
8. Obtain saliva sample for virus isolation (PCR/culture).
9. Obtain oral fluid for serology (CIR site only).
10. Review pregnancy prevention and continued use of barrier contraceptives.

*Whole blood/serum virology will be done only for those subjects who had detectable ZIKV in the blood at Study Day 16.

Study Day 28 (\pm 2 days from 28 days following test article administration)

1. Perform interim history, including sexual history, and focused physical exam, concentrating on any acute complaints.
2. Record vital signs.
3. Obtain approximately 50 mL of blood for immunology (serum, plasma, PBMCs), PAXGene and virology* from serum and whole blood (PCR/culture).
4. Obtain clean-catch urine for virus isolation* (PCR/culture).
5. Obtain cervico-vaginal secretion or semen sample for virus isolation* (PCR/culture). (Cervico-vaginal cup may be inserted at home by the volunteer prior to presentation to the clinic).
6. Obtain saliva sample for virus isolation* (PCR/culture).
7. Obtain oral fluid for serology (CIR site only).
8. Perform serum β -HCG testing (females only).
9. Review pregnancy prevention and continued use of barrier contraceptives.

*Whole blood/serum/CSV/semens/saliva/urine virology will be done only for those subjects who had detectable ZIKV in the blood at Study Day 21.

Study Day 35 (\pm 2 days from 35 days following test article administration)

1. Perform interim history, including sexual history, and focused physical exam, concentrating on any acute complaints.

2. Record vital signs.
3. Collect 8 mL blood for whole blood/serum virus isolation* (PCR/culture). Assays will be performed only for those subjects who had detectable ZIKV in the blood at Study Day 28.
4. Obtain clean-catch urine for virus isolation* (PCR/culture).
5. Obtain cervico-vaginal secretion or semen sample for virus isolation* (PCR/culture). Cervico-vaginal cup may be inserted at home by the volunteer prior to presentation to the clinic).
6. Obtain saliva sample for virus isolation* (PCR/culture).
7. Perform serum β -HCG testing (females only).
8. Review pregnancy prevention and continued use of barrier contraceptives with all subjects.

*Whole blood/serum/CSV/semen/saliva/urine virology will be done only for those subjects who had detectable ZIKV in the blood at Study Day 28.

Study Day 56 (\pm 3 days from 56 days following test article administration)

1. Perform interim history, including sexual history, and focused physical exam, concentrating on any acute complaints.
2. Record vital signs.
3. Obtain approximately 40 mL of blood for immunology (serum, plasma, PBMCs)/serum virus isolation* (PCR/culture).
4. Collect 3 mL blood for whole blood virus isolation* (PCR/culture). Assays will be performed only for those subjects who had detectable ZIKV in the blood at Study Day 35 or 49.
5. Obtain clean-catch urine for virus isolation* (PCR/culture).
6. Obtain cervico-vaginal secretion or semen sample for virus isolation (PCR/culture)*. Cervico-vaginal cup may be inserted at home by the volunteer prior to presentation to the clinic).
7. Obtain saliva sample for virus isolation* (PCR/culture).
8. Obtain oral fluid for serology (CIR site only).
9. Perform serum β -HCG testing (females only).
10. Male volunteers: Review pregnancy prevention and continued use of barrier contraceptives.

*Whole blood/serum/CSV/semen/saliva/urine virology will be done only for those subjects who had detectable ZIKV in the blood at Study Day 49.

Study Day 70 (\pm 3 days from 70 days following test article administration)

1. Perform interim history for interim complaints. (Physical exam is optional).

2. Record vital signs.
3. Collect 8 mL blood for whole blood/serum virus isolation* (PCR/culture). Assays will be performed only for those subjects who had detectable ZIKV in the blood at Study Day 49 or 56.
4. Obtain clean-catch urine for virus isolation* (PCR/culture).
5. Obtain cervico-vaginal secretion or semen sample for virus isolation* (PCR/culture). (Cervico-vaginal cup may be inserted at home by the volunteer prior to presentation to the clinic).
6. Obtain saliva sample for virus isolation* (PCR/culture).
7. Obtain oral fluid for serology (CIR site only).
8. Perform serum β -HCG testing (females only).
9. Male volunteers: Review pregnancy prevention and continued use of barrier contraceptives with all subjects.

*Whole blood/serum/CSV/semen/saliva/urine virology will be done only for those subjects who had detectable ZIKV in the blood at Study Day 56.

Study Day 90 (\pm 7 days from 90 days following test article administration)

1. Perform interim history for interim complaints. (Physical exam is optional).
2. Record vital signs.
3. Obtain approximately 40 mL of blood for immunology (serum, plasma, PBMCs)/serum virus isolation* (PCR/culture).
4. Collect 3 mL blood for whole blood virus isolation* (PCR/culture). Assays will be performed only for those subjects who had detectable ZIKV in the blood at Study Day 56 or 70.
5. Obtain clean-catch urine for virus isolation* (PCR/culture). Assays will be performed only if Day 56 or 70 sample was positive.
6. Obtain cervico-vaginal secretion or semen sample for virus isolation*. Assays will be performed only if Day 56 or 70 sample was positive. (Cervico-vaginal cup may be inserted at home by the volunteer prior to presentation to the clinic).
7. Obtain saliva sample for virus isolation* (PCR/culture). Assays will be performed only if Day 56 or 70 was positive.
8. Obtain oral fluid for serology (CIR site only).
9. Perform serum β -HCG testing (females only).
10. Review pregnancy prevention.

*Whole blood/serum/CSV/semen/saliva/urine virology will be done only for those subjects who had detectable ZIKV in the blood at Study Day 70.

Study Day 120 (\pm 10 days from 120 days following test article administration)

1. Perform interim history for interim complaints. (Physical exam is optional)

2. Record vital signs.
3. Collect 8 mL blood for whole blood/serum virus isolation* (PCR/culture). Assays will be performed only for those subjects who had detectable ZIKV in the blood at Study Day 70 or 90.
4. Obtain clean-catch urine for virus isolation (PCR/culture)*. Assays will be performed only if Day 70 or 90 sample was positive*.
5. Obtain cervico-vaginal secretion or semen sample for virus isolation* (PCR/culture). Assays will be performed only if Day 70 or 90 sample was positive. (Cervico-vaginal cup may be inserted at home by the volunteer prior to presentation to the clinic)*.
6. Obtain saliva sample for virus isolation* (PCR/culture). Assays will be performed only if Day 70 or 90 sample was positive.*
7. Perform serum β -HCG testing (females only).
8. Review pregnancy prevention.

*Collection of blood, urine, cervico-vaginal secretion, semen, and saliva samples for virology will be done on Study Day 120 only if virus was recovered from the sample collected at the previous time-points (Day 70 or 90) or if virology results are not available.

Study Day 150 \pm 7 days: The subjects will be contacted, and pregnancy prevention will be reviewed.

Study Day 180 (\pm 14 days from 180 days following test article administration)

1. Perform interim history for interim complaints.
2. Perform focused physical exam.
3. Record vital signs.
4. Obtain approximately 40 mL of blood for immunology (serum, plasma, PBMCs)/serum virus isolation (PCR/culture). Virus isolation will only be performed for those subjects who had detectable ZIKV in the serum at Study Day 90 or 120.
5. Collect 3 mL blood for whole blood virus isolation (PCR/culture), if necessary. Assays will be performed only for those subjects who had detectable ZIKV in the blood at Study Day 90 or 120.
6. Obtain clean-catch urine for virus isolation (PCR/culture). Assays will be performed only if the Day 90 or 120 sample was positive*.
7. Obtain cervico-vaginal secretion or semen sample for virus isolation (PCR/culture). Assays will be performed only if Day 90 or 120 sample was positive. (Cervico-vaginal cup may be inserted at home by the volunteer prior to presentation to the clinic)*.
8. Obtain saliva sample for virus isolation (PCR/culture). Assays will be performed only if Day 90 or 120 sample was positive*.
9. Obtain oral fluid for serology (CIR site only).
10. Perform serum β -HCG testing (females only).

11. Review pregnancy prevention.

*Collection of urine, cervico-vaginal secretion, semen, and saliva samples and virology (urine, vaginal secretion, saliva) will be done on Study Day 180 only if virus was recovered from the sample collected at the previous time-points (Day 90 or 120) or if virology results are not available.

Note: Blood, urine, saliva, semen, and cervico-vaginal secretion samples will be collected at the indicated visits. PCR and/or viral culture will be performed on the samples collected at the indicated time points from Study Day 21 through Day 180 if the sample was positive on samples collected on at least one of the previous time-points. If a sample has been negative for 2 consecutive time-points from Study Day 21 onward, then PCR/culture for ZIKV will not be performed on future samples unless there is an indication that the sample may be intermittently positive and additional samples need to be tested. Samples will be collected from all subjects through Study Day 90 because identifying which subjects may not require a sample would unblind the treatment assignment. After Study Day 90, if the samples at the 2 previous time points were negative then saliva, cervico-vaginal secretions, blood, semen, and urine will not be collected for virus isolation.

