Transmission via mosquito vector remains the principal driving force of ZIKV infection and disease. *Aedes* mosquitoes, particularly *Aedes aegypti*, are thought to be the primary vector for ZIKV [17, 18]. Complicating ZIKV control programs, there have been several reports of sexual transmission of ZIKV [19-24]. Although cases of sexual transmission have occurred, it appears to play a minor role in transmission as there have been only 52 documented cases of sexually acquired ZIKV resulting from a total of 5,460 travel-associated ZIKV cases in the United States (<1% of ZIKV cases) as of January 2, 2019, (Zika cases in US, accessed May 28, 2019) and it is not thought to contribute significantly to transmission [25]. All but 2 cases of sexual transmission have been from male to female. ***There has been only one report of female-to-male ZIKV transmission*** and one report of male-to-male ZIKV transmission [26, 27]. In all but one of the cases of sexual transmission, ZIKV has been transmitted from a ***symptomatic person*** to his partner. ***Transmission has occurred during or just after symptomatic illness***. In only one documented case has ZIKV been transmitted from an asymptomatic person to his partner [28]. There have been few longitudinal studies evaluating the sites and duration of ZIKV shed in bodily fluids [29, 30]. ZIKV ribonucleic acid (RNA) has been detected in semen by RT-PCR for 2 - 6 months after symptoms have developed [31-33]. However, to date, the longest interval between onset of symptoms and recovery of infectious ZIKV from semen is 69 days [34]. Studies have demonstrated that a minority of ZIKV-infected men shed ZIKV in semen. Mead *et al.* found ZIKV by RT-PCR in 60/184 men (33%) and found ZIKV by RT-PCR in only

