4 SELECTION AND ENROLLMENT OF SUBJECTS

Subjects must meet all eligibility criteria to be enrolled in the study. Because male-to-female sexual transmission of ZIKV is by far the most common pattern of sexual transmission, all male volunteers enrolled in the study must agree to use barrier contraception through Study Day 90 (per CDC guidance) post-enrollment. Female volunteers must use barrier contraception through Study Day 56 (per CDC guidance). Men will be enrolled to quantify the shedding of infectious ZIKV in semen. These data will better assess the risk of male-to-female transmission. Because ZIKV infection during pregnancy can be catastrophic to the fetus, female volunteers of childbearing potential will be required to use reliable methods of contraception, which include hormonal birth control (implantable, hormonal patch, NuvaRing®, oral contraception, Depo-Provera injection, etc.), IUD, or surgical sterilization (documented hysterectomy, tubal ligation or tubal coil; surgical sterilization procedures must be at least 3 months prior to inoculation) following CDC recommendations. Barrier contraception alone will not be considered a reliable method of birth control. Females who are postmenopausal (as defined as at least 1 year since last menstrual period); and females who exclusively have sex with females (and have no intention of conceiving a child during the study) are not considered to be of childbearing potential. Female volunteers on hormonal birth control must not be on medications or other agents that decrease the effectiveness of hormonal birth control.

To reduce the potential risk of transmission, ALL male subjects will be required to use barrier contraception through Study Day 90 and all female subjects will be required to use barrier contraception through Study Day 56 in accordance with CDC guidance. This includes females who exclusively have sex with females, females who are post-menopausal, and subjects who have undergone surgical sterilization.

Should a potential volunteer wish to use hormonal contraception or an IUD, study staff will refer her to a provider who can discuss the available contraception options with the subject. The study will pay for any costs of hormonal contraception not covered by insurance for the duration of the study and for the cost of placement of an IUD not covered by insurance if the subject decides she wants to enroll in the study and would like to use one of these methods of contraception.

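### If the closing Note of Section 6.4.1.2 governs, semen collected through Day 90 is assayed only after an earlier positive, so late-starting or intermittent shedding can go undetected

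*Combined protocol and SAP*

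**What the plan says.** The Note at the end of Section 6.4.1.2 sets the testing rule for Day 21 to Day 180. A sample is assayed "if the sample was positive on samples collected on at least one of the previous time-points". The stopping rule follows: "If a sample has been negative for 2 consecutive time-points from Study Day 21 onward, then PCR/culture for ZIKV will not be performed" on later samples, "unless there is an indication that the sample may be intermittently positive and additional samples need to be tested". No criterion is given for such an indication. Collection is wider than testing: "Samples will be collected from all subjects through Study Day 90", and the reason given is that selective collection would reveal treatment assignment.

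The Note does not say in so many words that the earlier positive must be in the same fluid. That is the natural reading, and the Day 90, 120 and 180 visit items apply it that way.

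The visit lists in the same section do not match the Note:
- **Day 21.** Only blood carries a condition ("Whole blood/serum virology will be done only for those subjects who had detectable ZIKV in the blood at Study Day 16"). Semen is listed for PCR/culture without one. Table 1 is flattened in the text, but it shows six unbracketed semen marks, which fits Days 0, 4, 8, 12, 16 and 21.
- **Days 28, 35, 56, 70 and 90.** Footnotes make semen assays depend on virus in the blood at an earlier visit. The Day 56 footnote relies on Day 49, which has no entry in the detailed procedures or in Table 1.

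The Precis and Section 2.1 place the quantity, frequency and duration of virus in semen under the primary objective. Section 4 gives the purpose of the male cohorts: "Men will be enrolled to quantify the shedding of infectious ZIKV in semen".

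**The concern.** A man whose semen is negative at every visit before the condition starts is not assayed again under the Note, so a first positive after that point cannot be seen. A man who sheds intermittently can have two chance negatives and drop out of testing while still shedding. The exception for intermittent positivity can be triggered only by results already in hand, because samples that are no longer assayed give no new indication.

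Skipping an assay can remove a positive but never add one. If the figures are built from the assayed samples alone, any error makes shedding look rarer or shorter. These are the quantities that cohorts 3 and 4 were opened to measure, and they bear on how the risk of sexual transmission is judged. With 20 ZIKV-inoculated men and roughly a third expected to shed RNA, one misclassified man is a large share of the shedders.

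**Working it through.** The documents give no figure for the effect of this rule, so there is nothing to reproduce. The calculations below are illustrations, and the assumed inputs are marked.

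**1. Semen assayed before any condition applies.** After inoculation, Section 6.4.1.2 lists semen on Days 4, 8, 12 and 16. Day 21 is added if the Day 21 visit list governs. The cut is therefore Day 16 or Day 21.

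**2. Late start.** Section 1.3.2.3 (Table 5, cohort 1) gives the mean day of first PCR detection as 11.5 in urine and 10.7 in cervico-vaginal secretions. Assume that semen behaves similarly, with normally distributed onset and an SD of 3 to 5 days. The share starting after the cut is P(Z > (cut − mean)/SD).
- Day 16 cut, lowest: (16 − 10.7)/3 = 1.77, giving 4%.
- Day 16 cut, highest: (16 − 11.5)/5 = 0.90, giving 18%.
- Day 21 cut, lowest: (21 − 10.7)/3 = 3.43, giving 0.03%.
- Day 21 cut, highest: (21 − 11.5)/5 = 1.90, giving 2.9%.

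Table 7 (cohort 2a) has column labels that do not fit its values. Read as mean peak, peak, onset and duration, it puts urine and cervico-vaginal onset at Days 8.0 and 8.5. The Day 16 tail is then 0.4% ((16 − 8.0)/3 = 2.67) to 6.7% ((16 − 8.5)/5 = 1.50). Saliva onset in the same table is Day 10.8, close to the cohort 1 values.

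**3. Effect on the proportion shedding.** Section 1.1 cites 60/184 = 33% of men with RT-PCR-positive semen. The recorded proportion is 0.33 × (1 − late share).
- Day 16 cut: 0.33 × 0.96 = 32% down to 0.33 × 0.82 = 27%.
- Day 21 cut: no lower than 0.33 × 0.97 = 32%.
- In men: 20 × 0.33 = 6.6 shedders, of whom 0.04 × 6.6 ≈ 0.3 to 0.18 × 6.6 ≈ 1.2 would be missed with the Day 16 cut.

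**4. Intermittent detection.** Take a man already under test who sheds RNA to Day 90. Assume each sample is positive independently with probability p, and that the exception is not used. Testing stops before Day 90 if two consecutive negatives occur among Days 21, 28, 35, 56 and 70. The chance of no such run in n visits is

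a(n) = p·a(n−1) + p(1−p)·a(n−2), with a(0) = a(1) = 1.

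For p = 0.8: a(2) = 0.960, a(3) = 0.928, a(4) = 0.896, a(5) = 0.865, so the chance of stopping is 0.135.

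| p (assumed) | 1 − a(5) |
|---|---|
| 0.8 | 14% |
| 0.7 | 27% |
| 0.6 | 43% |
| 0.5 | 59% |

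As a guide to p, the same cited study found 174 of 1,230 semen samples positive. With equal sampling per man this is 174/(1,230 × 60/184) = 0.43 per sample in men who were ever positive. That includes samples taken after clearance, so 0.5 to 0.8 during shedding is a reasonable range.

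**5. Number of assays skipped.** Days 21, 28, 35, 56, 70 and 90 are six visits. The most is 20 men × 6 = 120. If two thirds of the men never test positive, 120 × 2/3 = 80.

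**The case against.** The strongest reply is that the rule costs little for infectious virus. In one study cited in Section 1.1, culture-positive semen was found only within 30 days of illness and only at 7 log10 RNA copies/mL or more. In another, all but one culture-positive sample came within 15 days of symptom onset. Samples with that much RNA are unlikely to give two chance PCR negatives. This largely stands, and it means that the recursion bears mainly on low-level RNA duration. It does not dispose of the point: Days 21 and 28 lie inside the 30-day window, the same section reports that "the longest interval between onset of symptoms and recovery of infectious ZIKV from semen is 69 days", and the objectives ask for RT-PCR as well as culture.

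The second reply is that the Day 21 visit list leaves semen ungated, so the late-start loss is small. That stands if the visit list governs.

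The third is that the Day 28–70 footnotes, with their blood condition, may govern instead, so that this rule would not operate at those visits. That is possible, but a condition on blood is likely to be stricter for semen. The longest whole-blood PCR duration in cohort 1 was 15 days from a mean onset of Day 4.2, which ends at about Day 18 (4.2 + 15 − 1). The batch step proposed here would cover that case too.

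Three stronger readings are tempting but not supported:
- **That unassayed samples are scored as negative.** The documents give no scoring rule for a sample that was collected but not assayed. Section 9.5.2 deals only with missed visits.
- **That the intermittency exception can never operate.** A positive-negative-positive pattern in samples already assayed could trigger it. The fair criticism is that the trigger is undefined.
- **That a man missed in this way is certainly not sampled at Days 120 and 180.** The Note ends collection after two negatives, and an unassayed sample is not a negative. The Day 120 and 180 footnotes also allow collection when virology results are unavailable. Loss at those visits is possible, not certain.

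**Conclusion.** The point holds in conditional form. If the Note governs and refers to the same fluid, semen is not assayed from Day 21 (or Day 28) without an earlier positive semen sample. Testing also ends after two negatives unless an undefined exception is invoked. Late-starting or intermittent shedding can therefore go undetected in samples that were collected, and the error runs only downward.

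The late-start effect is modest: 4–18% of shedders with a Day 16 cut, and 3% or less with a Day 21 cut. It rests on borrowing onset days from other fluids in women and on an assumed SD. The intermittent effect is larger, at 14–59%. It applies only to men shedding RNA to Day 90, with independent detection of 0.8 to 0.5 and the exception unused. The main consequence is for RNA duration. A reader should not infer that the infectious-virus findings are seriously compromised, because the cited studies found infectious virus in semen mostly within 30 days.

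This is a cheap improvement. It does not invalidate an exploratory study whose specimens are stored (Section 8.3).

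**What to change.** Keep the real-time rule and add one batch step for cohorts 3 and 4:
1. Once a block has reached Day 90 and is unblinded (Section 3.1.6), run RT-PCR on every stored, unassayed Day 21–90 semen sample from ZIKV recipients, and culture each PCR-positive sample.
2. Base the proportion shedding and the last positive day on this complete series.
3. State that any sample still unassayed is not tested (censored), never negative.
4. Treat pending batch results as unavailable virology results when deciding on Day 120 and Day 180 collection.
5. Define what counts as an indication of intermittent positivity.
6. Reconcile the Note with the Day 21 visit list and with the blood-based footnotes at Days 28–90, including the reference to Day 49.

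The cost is about 80 to 120 RT-PCR assays, plus culture of the positives and some use of stored sample. No visits or subjects are added through Day 90, and blinding is unaffected. The shedding figures may become somewhat less favourable.
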